FeNO	Fractional exhaled nitric oxide concentration
FEV1	Forced Expiratory Volume at 1 Second
FVC	Forced Vital Capacity
GCP	Good Clinical Practice
GOLD	Global Initiative for Chronic Obstructive Lung Disease
H	Hours
HFG	Humanforschungsgesetz (HFG = HRA)
HFV	Humanforschungsverordnung (HFV = HRO)
HRA	Federal Act on Research involving Human Beings
HRO	Ordinance on Human research with the exception of clinical trials
ICS	Inhaled corticosteroids (e.g. Budesonid, Fluticasonefuroat, Fluticasonepropionate)
LAMA	Long acting muscarinic antagonist (e.g. Aclidinium, Umeclidinium, Glycopyrronium, Tiotropium)
LABA	Long acting β -2 agonist (e.g. Formoterol, Indacaterol, Salmeterol, Olopatadine, Vilanterol)
MSMS	Tandem mass spectrometry
PI	Principal Investigator
PTR-MS	Proton-transfer reaction - mass spectrometry
SABA	Short acting β -2 agonist (e.g. Terbutaline, Salbutamol)
SAE	Serious Adverse Events
SAMA	Short acting muscarinic antagonist (e.g. Ipatropium)
SESI-HRMS	Secondary electro-spray ionization high resolution mass spectrometry
SIFT-MS	Selected ion flow tube - mass spectrometry
SNCTP	Swiss National Clinical Trial Portal
SOP	Standard Operating Procedure
TMF	Trial Master File
USZ	UniversitätsSpital Zurich
V	Version
VOC	Volatile Organic Compounds
WHO	World Health Organisation

STUDY SYNOPSIS

Sponsor	[name]. med. [name]
Study Title	MOLECULAR BREATH PRINT OF COPD PATIENTS WITH EXACERBATIONS DESPITE TRIPLE INHALATIONAL THERAPY (TripleEX)
Study ID	Not yet available
Protocol Version and Date	Version 1.0 of 27.05.2020
Trial registration:	Not yet registered (SNCTP, clinicaltrials.gov)
Study category and Rationale	Risk category A according to HFV
Background and Rationale	
COPD is an inflammatory and progressive disease of the lungs and airways primarily characterized by irreversible airflow limitation. COPD is the third leading cause of death worldwide.(1) On-line breath analysis in COPD would allow continuous monitoring of metabolic health, disease progression, and medication in short time intervals. Results are obtained without delay which is of high importance in situations like COPD exacerbations.(2) The findings of a recent matched case control study in patients with frequent vs patients without frequent COPD exacerbations (3) provided data on metabolic breath-prints using untargeted real-time mass spectrometry in COPD. The study showed that real-time breath analysis by mass spectrometry allows distinguishing patients with frequent exacerbations from patients without frequent exacerbations on the basis of molecular analysis. The study provided biochemical insights in COPD patients at risk for exacerbations. However, because the study was performed in between COPD exacerbations (in a stable phase) it provided no information on biochemical processes during an actual COPD exacerbation. The identification of molecular changes during a COPD exacerbation could help to optimize treatment, identify new therapeutic targets and, is perhaps of diagnostic value.
 
GOLD guidelines recommend treating symptomatic COPD patients with frequent exacerbations with a triple inhalational therapy i.e beta-2-sympathicomimetics, anticholinergics and steroids (e.g. Trelegy®).(4) However, despite triple inhalational therapy a substantial number of patients continues to have exacerbations and thus are at high risk for disease progression, morbidity and mortality.(5) Some of these patients have elevated levels of eosinophils and may therefore, in theory, be eligible candidates for antibody treatment (e.g. with IL-5 blocking compounds such as Mepolizumab).(6) However, apart from eosinophil counts there is very little information on biochemical processes in COPD patients with exacerbations despite triple inhalational therapy. Thus, the identification of molecular changes could help to better understand relevant pathways and furthermore to identify new therapeutic targets. Particularly those patients who are most likely to respond to an antibody therapy would benefit.

Objective	The objective of this study is to determine specific molecular breath patterns by secondary electrospray ionisation mass spectrometry (SESI-HRMS) during and 8 weeks after a COPD exacerbation. Furthermore, breath patterns will be assessed for correlation and association to clinical outcomes and treatment.

Outcomes	
Primary Outcome Measure The primary outcome will be the change in exhaled breath metabolites during vs after COPD exacerbation.
 
Secondary Outcome Measures Correlation of breath metabolites with symptoms (mMRC and CAT®), inflammation markers (CRP and eosinophils, exhaled NO), causative agents (sputum microbiology and viral swabs) and treatment (inhalational drugs, steroids, antibiotics).

Study design	40 patients with COPD (staged according to GOLD recommendations, aged ≥ 18 years) on adherent triple inhalational therapy are to be included in a longitudinal study. Patients will undergo two measurements of exhaled breath; at baseline during a hospitalization due to COPD exacerbation and 8 weeks after the COPD exacerbation. Real-time breath analysis will be performed using SESI-HRMS coupled to a Q-exactive Orbitrap mass spectrometer (Thermo Fisher).
Inclusion criteria (inclusive) for all participants	
 • Informed Consent • age ≥ 18 years • staged according to GOLD recommendations • GOLD stage 2-4, risk groups A-D • hospitalization due to COPD exacerbation • subjects adherent to triple inhalational therapy (β-2-sympathomimetics, anticholinergics, steroids) • suitable for follow-up assessment • <48 hours after initiation of antibiotic therapy or systemic steroid therapy
Exclusion criteria (exclusive) for all participants	
 • physical or intellectual impairment precluding informed consent or protocol adherence • known pregnancy • congenital defects with direct impact on central metabolism e.g. amino acid metabolism defect • uncontrolled diabetes (e.g. HbA1c $>11\%$ or Glc $>20\text{mmol/l}$). • acute or chronic pulmonary disease other than COPD • renal failure or renal replacement therapy (GFR $< 15\text{ mL/min}$)
Number of Participants	N = 40
Study Duration	01.08.2020 – 31.07.2023

Investigators from University Hospital Zurich	
[name]. med. [name], Pulmonary Division, University Hospital Zurich, [name], Switzerland. [contact]
 
[name], RPh, Pulmonary Division, University Hospital Zurich, [name], Switzerland. [contact]
 
[name], Pulmonary Division, University Hospital Zurich, [name], Switzerland. [contact]
 
[name], Pulmonary Division, University Hospital Zurich, [name], Switzerland. [contact]

Study Centre	Pulmonary Division, University Hospital Zurich, [name], Switzerland
Statistical Considerations	
To test the hypothesis if there is a significant difference in the values of exhaled metabolites during and after COPD exacerbation, we will perform a paired-sample t-test to evaluate differential concentrations of such metabolites. False discovery rate and q-values will be subsequently computed as defined by Storey.(7) Well-established data reduction techniques such as principal component analysis will be used for visualization purposes. Finally, high mass resolution/ high mass accuracy data obtained will allow us to query online databases (e.g., human metabolome database) to provide tentative identification of the subset of most informative exhaled compounds. The pre-processing of the raw mass spectra and the statistical analysis will be implemented using MATLAB (MathWorks, Massachusetts, US).

GCP Statement	
This study will be conducted in compliance with the protocol, the current version of the Declaration of Helsinki(8), the principles of Good Clinical Practice and as well all national legal and regulatory requirements in Switzerland.

2. BACKGROUND AND RATIONALE

2.1 The role of exhaled breath analysis

The ancient Greeks already knew that using exhaled breath as an indicator of disease can be revealing.(9) The famous physician Socrates mentioned characteristic smells for different types of diseases such as a sweet smell in diabetes, a fishy smell in patients with liver problems, a urine-like smell in patients with kidney problems, or a putrid smell in patients with a lung abscess.(10) The primary opportunity of using exhaled breath as source for biomarker discovery is the ease with which breath can be collected for analysis (Figure 1). Patients are only required to exhale into a device or container and recent technological advancements have enabled a real-time analysis of exhaled breath, where data are available on the spot. Breath analysis offers a unique opportunity to non-invasively retrieve potentially unlimited sampling of relevant information on the ongoing internal biochemical processes, as parts of the most volatile components of blood reach the gas phase and are subsequently exhaled (e.g. detection of ethanol in breath).(11) Simple methods of breath analysis have made use of this, e.g. for the assessment of bronchial inflammation by measuring fractional exhaled nitric oxide (FeNO).(12) Despite these advantages of exhaled breath testing, its use in clinical practice is still limited. This is mostly due to a lack of thoroughly validated techniques.

[figure not shown]

Figure 1: Composition and origin of exhaled breath

2.2 Exhaled breath analysis by mass spectrometry

Analysis of exhaled breath gives biochemical information about the metabolism and the pathophysiological state. Chemical analysis of exhaled breath with mass spectrometry identified numerous volatile organic compounds (VOCs) [low molecular weight-components: < 500 Dalton (Da)].

The origin of these VOCs is diverse. VOCs can either be endogenous (arise from the respiratory tract), systemic (passing the blood-air barrier) or can be of exogenous origin (inhaled/exhaled environment air).⁽²⁾ The alveoli are intimately connected with the systemic circulation through the alveolar capillaries and its large blood-gas-interface. It was demonstrated that exhaled human breath contains a molecular fingerprint (also referred to as breathprint⁽⁹⁾). Breath composition changes during the course of the day (intra-individual variations). These temporal fluctuations may reflect circadian changes (13-15). Despite these changes, it was shown that each individual shows a distinct breathprint stable in time (individual core pattern of volatile and semi-volatile metabolites)⁽¹⁶⁾. The findings of preliminary studies by others and our group suggest that diseases of the airways such as e.g. chronic obstructive pulmonary disease

(COPD)(17, 18) may be diagnosed by a specific exhaled breath pattern.

2.3 Chronic Obstructive Pulmonary Disease (COPD)

COPD is an inflammatory and progressive disease of the lungs and airways primarily characterized by irreversible airflow limitation. COPD is the third leading cause of death worldwide.(1) Its prevalence among heavy smokers can reach up to 50%. According to the GOLD guidelines (Global Initiative for Chronic Obstructive Lung Disease) the diagnosis of COPD can be established by a fixed ratio of post-bronchodilator forced expiratory volume (FEV1) and forced vital capacity (FVC) below 0.7 measured by spirometry (see <http://www.goldcopd.org>). The severity of airflow limitation is graded according to the percentage of FEV1 predicted (GOLD stage I-IV). Furthermore severity of symptoms and risk of exacerbation is categorized by the risk groups A - D. This functional definition has been used to characterize the disease for many years. However, the degree of airflow limitation is only one aspect of the disease and COPD is being recognized as a heterogeneous disease, which requires tailored therapeutic approaches.(19) While the disease course involves a slow progressive deterioration in airflow, it is punctuated by exacerbations (acute deterioration of the patient's respiratory symptoms, i.e. worsening of dyspnea, cough and/or increased sputum production), many of which are serious, requiring hospitalization, and are associated with high mortality and extensive costs. The risk for exacerbations increases with higher GOLD stage.(20-22) After the second episode of severe exacerbation, the course of COPD is often associated with a rapid decline in health status. Furthermore, the mortality risk increases in the weeks following every severe exacerbation (23). Because of the complexity of COPD the disease management is mainly characterized in supporting prevention and maintenance therapy, stable COPD management and exacerbation management.

2.4 Exacerbation

An exacerbation of COPD is defined as an acute worsening of respiratory symptoms that results in additional therapy.(24, 25) COPD exacerbations are complex events usually associated with increase in airway inflammation, increased mucus production and marked gas trapping. These changes contribute to increased dyspnea which is the key symptom of an exacerbation.(4)

Exacerbations are classified as:

- Mild (treated with short acting bronchodilators only, SABDs)
- Moderate (treated with SABDs plus antibiotics and/or oral corticosteroids)
- Severe (patient requires hospitalization or visits the emergency room). Severe exacerbations

may also be associated with acute respiratory failure

During a COPD exacerbation, the worsening of the symptoms usually lasts between 7 to 10 days, but some events may last longer. It is well established that COPD exacerbations contribute to disease progression.(26) Disease progression is even more likely if recovery from exacerbations is slow.(27) Exacerbations can also cluster in time and once COPD patients experience an exacerbation, they will show increased susceptibility to further events.(20, 28) Depending on the frequency of exacerbations, COPD patients are divided into infrequent (0-1 exacerbations within the last 12 months) and frequent exacerbators (2 or more exacerbations within the last 12 months). Identifying COPD patients at risk for exacerbations, and especially frequent exacerbations, would be highly desirable to prevent further deterioration of early disease stages.

2.5 Exhaled breath analysis in COPD

Breath analysis in COPD is attractive because breath is available in nearly unlimited quantities. The analysis is non-invasive, and it presents no burden to the subject being measured. On-line breath analysis in COPD would allow continuous monitoring of metabolic health, disease progression, and medication in short time intervals. Data are obtained immediately which is of high importance in situations like COPD exacerbations.(2)

The diagnostic “gold standard” for COPD is based on spirometry and subjective symptom assessments, similar to asthma with respective COPD guidelines.(29) As it is primarily a disease of the lungs, a high number of breath-analysis studies are available for COPD; however, only a minority of the studies employed on-line methods.(30) Most studies used a case-control design with an untargeted approach in order to identify putative discriminative markers for the disease or disease severity. Three studies used ion mobility separation to identify COPD-specific biomarkers in a cohort of 119, 130, and 96 patients, respectively.(31-33) While two studies reported a 70–79% accuracy in the diagnosis of COPD (based on 6–10 VOCs), the other study reported 10 biomarkers, most of which were unidentified.(31) None of the identified substances overlapped between the two studies or was validated in an external cohort. Finally, two untargeted studies (17, 18) compared the breath print of COPD patients against healthy controls using SESI-MS with a real-time approach. Both studies yielded a Receiver Operating Characteristic (ROC) curve with an area under the curve of 0.88–0.91. However, in this case, with the aid of MS/ MS and complementary pre-separation methods some of the discriminate biomarkers could be identified and attributed to be metabolites of oxidative stress processes, such as fatty acids,

aldehydes, and amino acids.(17, 18) Most studies tried to control for the effects of smoking and there was evidence that lung capacity, body mass index, and certain inflammatory blood markers seem to play a role in the discrepancies observed between groups.(33, 34) In conclusion, studies on this topic are extremely heterogeneous and data processing and statistical methods are not standardized. As a result, none of the reported biomarkers overlaps between the studies and none of the biomarkers has been validated in an external cohort yet.

2.6 Rationale for the current study

The findings of a recent matched case control study in patients with frequent vs infrequent COPD exacerbations (3) provided data on metabolic breath-prints using untargeted real-time mass spectrometry in COPD. The study showed that real-time breath analysis by mass spectrometry allows distinguishing patients with frequent exacerbations from patients with infrequent exacerbations on the base of molecular analysis. Metabolite levels from the ω -oxidation pathway, namely ω -hydroxy, ω -oxo, and dicarboxylic acids, were consistently decreased in frequent exacerbators. Additionally, several new nitro-aromatic metabolites, which were significantly increased in frequent exacerbators, were identified. Thus, the study provided insights about ongoing biochemical processes in patients with COPD at risk for exacerbations. However, because the study was performed in between COPD exacerbations (in a stable phase) it provided no information on biochemical processes during an actual COPD exacerbation. The identification of molecular changes during a COPD exacerbation could help to optimize treatment, identify new therapeutic targets and, is perhaps of diagnostic value.

GOLD guidelines recommend treating symptomatic COPD patients with frequent exacerbations with a triple inhalational therapy i.e beta-2-sympathicomimetics, anticholinergics and steroids (e.g. Trelegy®).(4) However, despite triple inhalational therapy a substantial number of patients continues to have exacerbations and thus are at high risk for disease progression, morbidity and mortality. Some of these patients have elevated levels of eosinophils and may therefore, in theory, be eligible candidates for antibody treatment (e.g. with IL-5 blocking compounds such as mepolizumab).(6) However, apart from eosinophil counts there is very little information on biochemical processes in COPD patients with exacerbations despite triple inhalational therapy. Thus, the identification of molecular changes could help to better understand relevant pathways and furthermore help to identify new therapeutic targets. Particularly those patients who are most likely to respond to e.g. an antibody therapy would benefit from a deeper understanding of molecular mechanisms.

This will be the first study to investigate the acute effects of COPD exacerbations on molecular exhaled breath patterns assessed by SESI-MS. By identifying a distinctive breath pattern it may be possible to define biochemical processes specific of a COPD exacerbation and correlate it with causative agents, treatment and outcome.

2.7 Triple Inhalational Therapy in COPD

Triple therapy is most likely indicated in patients with COPD who are severely symptomatic, have moderate to very severe airflow obstruction and a history of frequent and/or severe exacerbations.(4) The step up in inhaled treatment to LABA plus LAMA plus ICS (triple therapy) can occur by various approaches.(35) This may improve lung function, patient reported outcomes and prevent exacerbations. Adding a LAMA to existing LABA/ICS improves lung function and patient reported outcomes, in particular exacerbation risk.(36-40) Double blind RCTs have reported benefits of single-inhaler triple therapy compared with LABA/LAMA combination therapy.(41, 42)

2.8 Role of eosinophils and targeting IL-5 in COPD

Novel approaches to COPD treatment focus on understanding and targeting molecular mechanisms of airway inflammation, airway obstruction, remodelling and lung destruction. The most promising biologic treatments at an advanced stage of development are agents blocking interleukin (IL)-5 or its receptor.(43) The inflammatory phenotype of COPD can be described as: 1) neutrophilic, 2) eosinophilic, 3) mixed eosinophilic and neutrophilic and 4) paucigranulocytic nature.(44) Neutrophilic airway inflammation is the most predominant type seen in COPD, but eosinophilic inflammation is present in up to 40% of COPD patients.(45) In particular eosinophils increase the risk of exacerbations and IL-5 expression.(45, 46) IL-5 expression is a key player in inflammatory processes of COPD. Therefore options such as targeting IL-5 with Mepolizumab/ Reslizumab or IL-5Ra with Benralizumab are encouraging. However, results of phase III clinical trials e.g. METREX(47), METRO(47), GALATHEA(48) or TERRANOVA(49) in eosinophilic COPD patients have not shown a breakthrough in exacerbation prevention. Breath analysis could lead to a deeper understanding of pathophysiological mechanisms of COPD exacerbations in context with IL-5 and thus help to find more suitable biomarkers and select those COPD patients who are most likely to benefit from IL-5 blocking therapy.

3. STUDY OBJECTIVES AND DESIGN

3.1 Hypothesis and primary objective

3.1.1 Hypothesis

Molecular breath patterns acquired by secondary electrospray ionization mass spectrometry (SESI-MS) are distinctively altered during COPD exacerbation.

3.1.2 Objective

The objective is to determine specific molecular breath patterns by secondary electro ionisation-mass spectrometry (SESI-MS) during and 8 weeks after a severe exacerbation requiring hospitalization. Furthermore, molecular breath patterns will be assessed for correlation and association to clinical outcomes and treatment.

3.2 Study Outcome

3.2.1 Primary Outcome

The primary outcome will be the change in exhaled breath metabolites during vs after COPD exacerbation.

3.2.2 Secondary Outcome Measures

Correlation of breath metabolites with symptoms (mMRC and CAT®), inflammation markers (CRP and eosinophils, exhaled NO), causative agents (sputum microbiology and viral swabs) and treatment (inhalational drugs, steroids, antibiotics).

3.3 Study Design

We will conduct a prospective, longitudinal, observational study including 40 patients with proven COPD staged according to GOLD recommendations and under adherent triple inhalational therapy. The treating physician will check during the general assessment the compliance to triple therapy treatment.

A study flow chart is presented in Figure 2

[figure not shown]

Figure 2: Study flow chart. COPD = Chronic Obstructive Pulmonary Disease; BA = Breath Analysis; GOLD = Global Initiative for Chronic Obstructive Lung Disease; * Breath analysis by SESI_MS; +steroids & antibiotics

4. STUDY POPULATION AND STUDY PROCEDURES

4.1 Project population and eligibility criteria

A population of subjects with COPD staged according to GOLD recommendations with exacerbation requiring hospitalization will be screened. Furthermore, only subjects adherent to triple inhalational therapy i.e beta-2-sympathicomimetics, anticholinergics and steroids are eligible. An exacerbation of COPD is defined as an acute worsening of respiratory symptoms that results in additional therapy.(4)

4.2 Inclusion criteria

- Informed Consent
- Age \geq 18 years
- GOLD stage 2-4, risk groups A-D
- hospitalization due to COPD exacerbation
- Defined exacerbation according to GOLD guidelines
- Subjects adherent to triple inhalational therapy (β -2-sympathomimetics, anticholinergics, steroids)
- Suitable for follow-up assessment
- <48 hours after initiation of antibiotic or steroid impulse therapy

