spectrometer by Thermo Fisher. This results in sensitive and selective, yet real-time, analysis of trace vapour species.(53) Our SESI-HRMS is situated in a separate, lockable room at the University Hospital Zurich. Access to the designated room is only permitted to members of the staff. Participants will be asked to refrain from eating, drinking, chewing gum, alcohol, tobacco, caffeine use or brushing their teeth at least 1 hour before the measurements will be performed. Room temperature and lighting will be set at the same level for all measurements. Participants will exhale through a disposable mouthpiece, into a heated tube (stainless steel, Silconert coated) (50 cm long, 4 mm in diameter) connected to the curtain AUX gas port of a Orbitrap spectrometer (Thermo Fisher, Waltham, Massachusetts, USA) that is provided by DBI. The sampling tube is surrounded with an isolated heating tape at 130 °C to prevent water condensation and to minimize losses of exhaled compounds onto the walls of the tube. While performing full exhalations, the subjects will keep the volume through the sampling line at 8L/min monitored by a digital flow meter. A nano electrospray plume (FIT, Madrid, Spain), provided by DBI, will be used, where compounds of exhaled breath get ionized and subsequently are mass analysed. The technique, by which breath is analysed in real time by injecting exhaled breath into electrospray plumes of pure solvent and thus causing ionization of relevant exhaled compounds(54-56), has been referred to as secondary electrospray ionization (SESI)(57). Breathprints will be collected in real-time recording six replicates through the mouthpiece. The raw mass spectra will be exported as mzXML files for further processing using MATLAB (Mathworks, Inc). The spectra of exhaled breath will be averaged. In this process, only the last few seconds (typically around 6 sec.) of each exhalation will be considered, thus the first part of the exhalation, which reflects mostly the dead space in the upper respiratory tract, will be excluded from the analysis. SESI-MS allows for real-time breath-printing by detection of both volatile and non-volatile trace components in breath without any sample pre-treatment. The de-identified mass spectrometric breath signatures of patients are subsequently analysed by DBI with AI algorithms for spectroscopic profiling.

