5. STATISTICS AND METHODOLOGY

5.1 Statistical analysis plan

For data processing, we will follow the same procedure as described in our previous studies [Gaugg, 2016]: raw mass spectra will be transformed to *.mzXML format using the online tool msConvert. The *.mzXML files will be imported into Matlab. Each mass spectrum is then interpolated (shape-preserving piecewise cubic interpolation method), mass calibrated using an iterative grid search algorithm, and the resulting spectra are centroided. To test the hypothesis that there is a significant difference in the values of exhaled metabolites during and after the exacerbation, we will perform a paired-sample t-test to

evaluate differential concentrations of such metabolites. False discovery rate and q-values will be subsequently computed as defined by Storey.(60) To account for instrumental drift (e.g., detector sensitivity), the mass spectra are normalized using standard methods such as interquartile range, total ion current. Well-established data reduction techniques such as principal component analysis will be used for visualization purposes. Finally, high mass resolution/high mass accuracy data obtained will allow us to query online databases (e.g., human metabolome database) to provide tentative identification of the subset of most informative exhaled compounds. The preprocessing of the raw mass spectra and the statistical analysis will be implemented using MATLAB (MathWorks, Massachusetts, US).

For correlation analysis, the Pearson's linear correlation coefficient and 95% bootstrap confidence intervals will be applied. Continuous data will be summarized by means (SD) or medians (quartiles) as appropriate. A two-sided p value of <0.05 will be considered to be statistically significant for all tests.

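### Visit 1 breath may be sampled after antibiotics or systemic steroids have started, so a feature driven only by acute treatment can be listed as an exacerbation feature

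*Combined protocol and SAP*

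**What the plan says.** - **Entry.** Section 4.2 includes patients "<48 hours after initiation of antibiotic or steroid impulse therapy"; the synopsis has "<48 hours after initiation of antibiotic therapy or systemic steroid therapy". Both are inclusion criteria.
- **Breath sampling.** Section 4.5.9 places Visit 1 within the hospital stay and Visit 2 about 8 weeks later. The Appendix labels Visit 1 day 0 without tying it to the start of therapy.
- **Definition.** Section 4.1: "An exacerbation of COPD is defined as an acute worsening of respiratory symptoms that results in additional therapy".
- **Primary outcome and test.** Section 3.2.1: "The primary outcome will be the change in exhaled breath metabolites during vs after COPD exacerbation". Section 5.1: "we will perform a paired-sample t-test", then Storey q-values. No q cut-off is given and the test has no treatment term.
- **Where treatment appears.** Section 3.1.2 puts association with treatment in the objective, and section 3.2.2 lists correlation with "treatment (inhalational drugs, steroids, antibiotics" among the secondary outcomes. Medication is recorded at both visits (section 4.5.2, Appendix). Section 5.1 plans to query databases to "provide tentative identification of the subset of most informative exhaled compounds".
- **Aim.** Sections 2.6 and 7.1 hope that processes specific to an exacerbation can be defined.

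**The concern.** By the plan's own definition, an exacerbation brings added therapy with it. If breath is taken after that therapy starts, and the therapy has stopped by Visit 2 (an assumption; the documents do not say), disease and treatment switch on and off together within each patient. Pairing removes stable patient traits, but not a factor that changes between the visits along with the disease. Q-values do not help either: they limit false differences, and a treatment-driven difference is real but wrongly attributed.

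Two kinds of feature are at risk. One is an endogenous metabolite shifted by steroids or antibiotics. The other is an ion from the drug itself or its metabolites, since section 4.5.7 says the method allows "detection of both volatile and non-volatile trace components in breath". At stake is whether the list can be read as exacerbation biology, which is what the rationale hopes for.

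**Working it through.** **1. What the 48 hours governs.** Sections 4.2 and 4.5.9 together give an entry limit counted from the start of therapy and a Visit 1 that may fall anywhere in the stay. Nothing visible joins the two, so time from first dose to breath has no stated upper limit. The criterion joins two drug classes with *or* and does not say which start counts when they differ. Checking eligibility needs a start time, so one is probably obtainable, but it is not named as an analysis variable.

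**2. The plan's own figure.** Section 5.2 fixes 40 complete pairs and states that no conventional calculation is possible. There is no power, effect size or SD to reproduce.

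**3. Chance that a treatment-only feature is called.** For a feature with no exacerbation effect, take the paired difference as D = δE + error. The error SD is 1; E = 1 if the patient was treated before the Visit 1 breath and is off treatment at Visit 2. The values of δ and the share exposed are assumed. With all 40 exposed, the t statistic is noncentral with 39 df and noncentrality δ√40; for δ = 0.5 this is 0.5 × 6.32 = 3.16, against critical values of 2.02 (p<0.05) and 3.56 (p<0.001). Partial exposure (10, 20 or 30 of 40) was simulated with 400,000 data sets per cell. The plan states p<0.05; p<0.001 is my stand-in for the stricter per-feature threshold that a q-value rule may imply.

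| Threshold | δ (SD) | 25% exposed | 50% | 75% | 100% |
|---|---|---|---|---|---|
| p<0.05 | 0.3 | 7% | 15% | 28% | 46% |
| p<0.05 | 0.5 | 11% | 32% | 62% | 87% |
| p<0.05 | 0.8 | 20% | 64% | 95% | >99% |
| p<0.001 | 0.3 | 0.2% | 0.7% | 2.3% | 6.4% |
| p<0.001 | 0.5 | 0.4% | 2.8% | 12% | 36% |
| p<0.001 | 0.8 | 1.1% | 12% | 52% | 92% |

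Patients still treated at Visit 2 would lose some or all of the shift, so these figures would fall.

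**4. Do q-values protect?** Simulation with 1,000 independent features (50 exacerbation-only, 50 treatment-only, 900 null), shift 0.8 SD, q<0.05, 300 runs per setting; all of these inputs are assumed.

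| Share exposed | 0% | 25% | 50% | 75% | 90% | 100% |
|---|---|---|---|---|---|---|
| Treatment-only feature called | 0.3% | 2.6% | 23% | 73% | 93% | 98% |
| Treatment-only share of list | 0.3% | 2.5% | 18% | 41% | 46% | 48% |

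True nulls stay near 5% of the list throughout, so the FDR does its own job. The 48% merely reflects the assumed 50:50 split of affected features; read the table for direction only.

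**5. Can the planned treatment correlation find these features?** A Pearson correlation with a treated/untreated indicator is equivalent to a two-sample t-test with noncentrality δ/√(1/a+1/b). For δ = 0.8 and 20 v 20 this is 0.8/√0.1 = 2.53. Power at an unadjusted 0.05 is 69% (20 v 20), 57% (30 v 10), 32% (36 v 4) and 19% (38 v 2). With all 40 treated the effect cannot be estimated. The check is weakest where misattribution is most likely.

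**6. Would a table of hits by exposure settle it?** Not without a caveat. For a treatment-only feature the true change in the unexposed is 0, but selection on the same patients biases their mean away from zero:

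| Threshold, δ, exposed/unexposed | Unexposed mean among hits | 95% CI covers 0 |
|---|---|---|
| p<0.001, 0.5 SD, 20/20 | 0.38 SD | 61–63% across runs |
| p<0.001, 0.5 SD, 10/30 | about 0.45 SD | 5% |
| p<0.05, 0.3 SD, 10/30 | 0.23 SD | 64% |
| p<0.05, 0.8 SD, 20/20 | 0.10 SD | 96% |

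The bias becomes small when exposure is common and the effect strong.

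**The case against.** The strongest reply is that the plan does what it says. The primary outcome is change during versus after, and the paired t-test estimates exactly that. The study is exploratory (section 5.2). The sentence about exacerbation-specific processes is hedged and goes on to mention correlation with treatment. Treatment association is in the objective and the secondary outcomes, medication is recorded twice, and identification may recognise some drug ions. If few patients were treated before breath, or drug effects are weak, little goes wrong.

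Much of this stands: the test is valid for its stated contrast, and the safeguards are real. What remains is that no text lets any of them qualify the primary list. The identification step does not mention administered drugs, and it could not flag an endogenous metabolite shifted by treatment.

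Three stronger readings are tempting and not supported:
- A reader might infer that treatment-only features *will* fill the list. The share exposed and the drug effect are undocumented, and the range in step 3 runs from negligible to near certain.
- A reader might take 48 hours as the longest exposure before breath. It is written as an entry criterion, so it neither caps the sampling time nor shows that sampling happens later.
- A reader might conclude that the primary test is wrong. The problem is attribution, not estimation.

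The legend of Figure 2 mentions steroids and antibiotics, but the figure is not available here, so nothing is inferred from it.

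**Conclusion.** The point holds as one of interpretation and should be addressed; confidence is medium. The design cannot separate an exacerbation from its acute treatment in patients already treated at the Visit 1 breath test, and nothing visible prevents or counts such exposure. The chance that a given treatment-only feature is called lies between 0.2% and over 99% across the assumed settings. This rests on normal paired differences, shifts of 0.3 to 0.8 SD, 25% to 100% exposed, and no exposed patient still treated at Visit 2. The proportion of reported hits that would be treatment-only cannot be stated from the documents.

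**What to change.** Care and the primary test stay as they are.

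1. Record date and time of the first systemic steroid dose, the first antibiotic dose and the Visit 1 breath test. Report, per class, how many patients were measured before any dose and how many still take the drug at Visit 2.
2. In the planned identification step, annotate ions matching the drugs administered and their known metabolites, and show them in a separate, visible table. Q-values stay as computed on all features.
3. Show the mean paired change by exposure (none, steroid only, antibiotic only, both) for all features. If only hits are shown, state beside the table that means and CIs for features selected on the same patients are biased away from zero, including in the unexposed, and cannot show that a feature is drug-free. Description only.
4. Unless the counts in item 1 show that essentially all patients were measured before any dose, word the conclusion as change during *exacerbation and its acute treatment*, and do not call features exacerbation-specific.
5. Reconcile the synopsis criterion and sections 4.2 and 4.5.9 on whether the 48 hours governs entry or breath sampling, and on which start counts when the two classes begin at different times.

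**Cost.** Three time fields on the CRF, one extended annotation step, one descriptive table and some SAP wording. Mass matching may misassign an endogenous ion of equal mass, which is why moved ions stay visible. The exposure table will be imprecise: the 95% half-width, t/√m, is 0.47 SD for 20 patients, 0.72 for 10 and 1.24 for 5. For an exposed-minus-unexposed difference it is 0.64 SD (20 v 20), 0.74 (30 v 10) or 0.97 (35 v 5), so seeing no difference would not rule out a drug effect. The conclusion also becomes more modest.
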